9.7.2 Analysis of treatment data

Duration and dose of the Adempas® treatment during the observation period will be calculated for each patient. The dose will be displayed at the different visits/time windows. The number of patients adding and removing various PH medications (including Adempas®) will be summarised using frequency tables.

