9.1 Study design

The EXPERT registry is a global, multicenter, prospective, uncontrolled, non-interventional cohort study documenting data from patients with PH treated with Adempas[®]. It is linked with the existing global COMPERA registry, a global academic multicenter prospective registry, which documents consecutive patients with the different forms of pulmonary hypertension (PH) treated with specific PAH drugs. For EXPERT the documentation in COMPERA will be extended to include additional Adempas[®]-specific data.

It is planned to include around 35 countries in the region Europe, Asia Pacific, Latin America.

The study will start after Adempas[®] has been authorized and made commercially available in the countries involved in the study.

All patients prescribed with Adempas[®] for a medically appropriate use, consent to participate, and fulfil the selection criteria are eligible for enrolment into the study. Patients will be followed up for an observation period of 1 up to 4 years (recruitment period 3 years). Patient's clinical information will be documented at time of the initial visit and approximately every three to six months according to local clinical practice thereafter. Data collection will continue until 30 days after the end of Adempas[®] therapy.

The decision on clinical management of the patient including the actual treatment duration will be determined solely by the physician.

The study ends 12 months after enrolment of the last patient

Serious adverse events will be followed up until resolution.

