9.5 Study Size

It is planned to enrol 900 patients in specialized centers with the expectation to include a significant proportion of patients newly starting Adempas® monotherapy. This sample size allows detecting at least three "uncommon" AEs (with a probability of 83%) with an incidence of 0.5% (5/1000) or more. This is in the range of "uncommon" AE (0.1%=1/1000 to 1%=1/100). If the sample size increases to 1130, at least three "uncommon" AEs with incidence of 0.4% or more can be detected with the same probability.

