9.7.4 Analysis of secondary outcome(s)

The secondary safety outcomes will be analyzed similar to the primary outcomes. Subgroup analyses will be conducted for selected secondary endpoints (e.g. 6 Minutes Walking Test, NYHA/WHO FC, hospitalization).

Analyses of adverse events will be conducted for PH subgroups (inoperable vs. post- surgery CTEPH patients, monotherapy vs. combination therapy PAH patients) .

Adverse events of interest will be analysed in detail. Adverse events of interest are

- Symptomatic hypotension
- Hemoptysis/ pulmonary haemorrhage

Further analyses of information on adverse events of interest as given by the detailed questionnaire and the AE page will be evaluated.

Kaplan Meier plots will describe the time until the individual events of interests

For the effectiveness variables summary statistics and changes form baseline will be calculated for

- 6 Minutes Walking Test,
- Borg Dyspnoea Index
- EO5D VAS
- Hemodynamic measurements
- Biomarkers

NYHA/WHO FC will be analyzed by frequency tables including changes from baseline.

The variables of hospitalization due to PH and drug utilization (reason and drug switch or interruption or discontinuation of Adempas®) will be analyzed by frequency tables and summary statistics.

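### Adempas discontinuation is to be reported as a crude percentage although planned follow-up runs from 1 to 4 years, so the figure mixes length of follow-up with persistence

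*Protocol*

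**What the plan says.** - **Follow-up (Protocol 9.1).** "Patients will be followed up for an observation period of 1 up to 4 years (recruitment period 3 years"; and "The study ends 12 months after enrolment of the last patient". The study end is common to all, so a patient's maximum follow-up is set by the enrolment date.
- **Outcome (8.2, 9.3.2).** How Adempas is used is a secondary objective. Discontinuation and its reason are listed among the secondary variables, under resource use.
- **Method for discontinuation (9.7.4).** Switching, interrupting and stopping Adempas, with the reason, "will be analyzed by frequency tables and summary statistics". Section 9.7.1 describes frequency tables as absolute and relative frequencies.
- **Method for treatment data (9.7.2).** Duration and dose of "treatment during the observation period will be calculated for each patient". The numbers of patients adding or removing PH drugs, Adempas included, "will be summarised using frequency tables".
- **Methods that allow for follow-up time.** Kaplan-Meier plots are named in 9.7.4 for the adverse events of interest only. Person-time rates are named in 9.7.3 for the primary safety events.
- **Interim analyses (9.7.1).** These are at least yearly and cover the primary and secondary objectives.

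**The concern.** Stopping a drug is a time-to-event outcome. A patient enrolled in the first month can be watched for almost four years, and one enrolled last for one year. The share who have stopped by study end depends on the stopping rate and on how long patients were watched, and a plain frequency table cannot separate the two.

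Three readings are at stake:
- The overall percentage cannot be read as discontinuation by any stated time on drug.
- Countries, regions or subgroups that enrol earlier would show more discontinuation with no difference in persistence.
- Successive yearly reports would show a rising percentage even if stopping behaviour never changed.

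The final-visit section (within 9.2.7) adds a complication. It separates regular end of observation from discontinuation of therapy, but its list of discontinuation reasons includes failure to follow up, centre closure and study termination. These can end observation without the drug being stopped, and a table of reasons would count them beside true stopping.

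**Working it through.** **The plan's own figure.** The only design figure is in 9.5: "It is planned to enrol 900 patients in specialized centers", to see at least three events "with a probability of 83%) with an incidence of 0.5% (5/1000) or more". The exact binomial tail for n = 900 and p = 0.005 is 82.7%, so the figure reproduces. For the alternative ("If the sample size increases to 1130", incidence 0.4%) it is 82.9%, which also reproduces. Neither bears on discontinuation, for which the protocol gives no rate.

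**Inputs.** From 9.1: recruitment over 3 years and study end 1 year after the last enrolment. Assumed: uniform enrolment, so maximum follow-up C is uniform on 1 to 4 years; a constant proportion a stopping per year, hazard h = -ln(1 - a); no other loss. Death is not separated from other stopping in this illustration.

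**Formula.** For follow-up uniform between c1 and c2 years:

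crude discontinued share = 1 - (e^(-h·c1) - e^(-h·c2)) / (h·(c2 - c1))

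**Case a = 20%** (h = 0.2231; e^(-h) = 0.8, e^(-2h) = 0.64, e^(-3h) = 0.512, e^(-4h) = 0.4096):

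- All patients (1 to 4 years): 1 - (0.8 - 0.4096)/(3 × 0.2231) = 1 - 0.583 = 42%
- First-year enrollees (3 to 4 years): 1 - (0.512 - 0.4096)/0.2231 = 54%
- Third-year enrollees (1 to 2 years): 1 - (0.8 - 0.64)/0.2231 = 28%
- Cut at year 1 (0 to 1 year): 1 - (1 - 0.8)/0.2231 = 10%
- Cut at year 2 (0 to 2 years): 1 - (1 - 0.64)/(2 × 0.2231) = 19%
- Cut at year 3 (0 to 3 years): 1 - (1 - 0.512)/(3 × 0.2231) = 27%
- Cut at year 4 (study end): 42%, as above

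**Range of assumed stopping rates.** The first patient enrolled has 4 years of follow-up, so the share is 1 - (1 - a)^4. The last has 1 year, so it is a.

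| Stopping per year (assumed) | Crude share, all | First enrolled | Last enrolled |
|---|---|---|---|
| 5% | 11.9% | 18.5% | 5.0% |
| 10% | 22.8% | 34.4% | 10.0% |
| 15% | 32.7% | 47.8% | 15.0% |
| 20% | 41.7% | 59.0% | 20.0% |
| 25% | 49.8% | 68.4% | 25.0% |
| 40% | 69.3% | 87.0% | 40.0% |

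**What a time-referenced summary would show.** At a = 20%, cumulative discontinuation is 20% at 1 year, 1 - 0.64 = 36% at 2 years and 1 - 0.512 = 49% at 3 years. In expectation these values are the same for every enrolment year and at every data cut that reaches the time point.

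**The case against.** **Detail belongs to the SAP, and the study is descriptive.** Section 9.7.1 leaves calculated variables and table layouts to the SAP, plans disposition by analysis time point, and calls the study non-confirmative. Section 8.2 gives indication and dose as examples of drug use and does not name persistence. A frequency table is also the ordinary display for reasons. All of this stands and keeps the point modest. It does not remove it: 9.7.4 names the method for discontinuation, and an SAP that followed it would inherit the weakness.

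**Observed duration is sound.** A reader might infer that cut-off durations are to be treated as complete. The text does not say so. Section 9.7.2 limits duration to the observation period, which is a valid measure of exposure and supplies the person-years in 9.7.3. Nor should mean observed duration (0.417/0.2231 = 1.87 years at a = 20%) be set against a lifetime mean of 1/0.2231 = 4.48 years. The latter extrapolates beyond a four-year study, and the plan does not claim to estimate it.

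**Cut-off is not certain to affect most patients.** A reader might assume that it does. The share still on drug at study end exceeds one half only if fewer than about 25% stop per year. The PAH mortality figures in section 7 (32% dead, or 58% alive, at 3 years) imply 12.1% or 16.6% per year. If death were the only reason for stopping, 73% or 64% would be cut off; other reasons lower this.

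**Enrolment date does not dominate.** A reader might conclude that the summaries reflect enrolment date more than persistence. Enrolment date explains about 24% of the variance in observed duration at 20% stopping per year. It passes one half only below about 8.6% per year, which is less than those mortality figures alone imply.

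**New and existing users are already separated** in 9.7.1. That helps, but follow-up still varies from 1 to 4 years within each group.

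**Conclusion.** The point holds for discontinuation. The named method gives a percentage that mixes length of follow-up with persistence and refers to no fixed time on drug. The direction does not depend on the assumed rate; the size does. At 20% per year, first- and third-year enrollees with identical persistence differ by 54% against 28%, and the yearly reports climb from 10% to 42%. These figures rest on uniform enrolment and a constant stopping rate, neither of which the protocol states.

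The consequence is limited to a descriptive secondary variable. The primary safety rates use person-time and are untouched. The change is worth making because it is cheap and replaces a stated method with one that can be interpreted.

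**What to change.** In 9.7.4, keep the frequency table of reasons and add:

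- **Newly starting patients:** cumulative incidence of Adempas discontinuation at fixed times since first dose (for example 6, 12, 24 and 36 months), with death as a competing event. Censor patients still on drug at last contact, whether observation ended regularly or through loss to follow-up, centre closure or study termination.
- **Existing users:** report separately, either by time since first dose with delayed entry at enrolment, or as discontinuations per person-year.

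In 9.7.2, label the duration summary as observed exposure, not persistence.

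The cost is a few sentences and one extra descriptive analysis. Start and stop dates are already collected (9.3.16), and the final visit already records why observation ended, so no new data are needed.

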9.7.3 Analysis of primary outcome(s)

The main goal of this global registry is to assess the long-term safety of Adempas® in real life clinical use. Incidences of treatment-emergent adverse events, serious adverse events and all-cause mortality will be calculated, including adverse events of interest. An adverse event is considered as treatment-emergent when it has started or worsened after first application of study medication up to 2 days after end of treatment with study medication.

For the events the 'raw' incidence proportion (regardless of the time each patient is treated), i.e. number of patients with events divided by the number of treated patients, will be presented as well as incidence rates, i.e. number of patients with events divided by the cumulative person-time on treatment (person-years) separately for incident and prevalent patients.

The statistics will be calculated for Adempas[®] and stratified for medically relevant subgroups, e.g.

- Age
- Gender
- Etiology (Dana Point Classification of PH)
- · Hepatic impairment at baseline
- Renal impairment at baseline
- WHO functional class/NYHA group at baseline
- According to e.g. 6 MWD thresholds >= 380 m versus < 380m at baseline
- Type of PH pre-treatment
- Concomitant medication use
- Systolic blood pressure at baseline

The subgroup 'Type of PH pre-treatment' will include the categories 'therapy-naïve', 'pre-treated with ERA', 'pre-treated with PDE5 inhibitors', 'pre-treated with prostacyclins' and 'pre-treated with Adempas[®].

The 'Concomitant medication use' subgroup categories will refer to e.g. 'concomitant ERA', 'concomitant PDE 5 inhibitors', 'concomitant prostacyclins' and 'concomitant oral anticoagulation' see section 9.3.16 Details will be found in the SAP.

A comprehensive list of medically relevant subgroups will be added to the SAP.

Tables which show the incidence proportion of adverse events overall and by MedDRA preferred term within the primary SOC will also be presented. Incidences of adverse events and serious adverse events starting more than 2 days after end of treatment will be tabulated separately.

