9.1.1 Primary endpoint(s)

The primary endpoints are:

- Incidence of adverse events/ serious adverse events
- Incidence of all-cause mortality

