9.7 Data analysis

9.7.1 Statistical considerations

Statistical analyses of this study will be of non-confirmative nature. This study is designed to support hypothesis generation.

All background variables and outcome parameters will be analyzed descriptively with appropriate statistical methods: categorical variables by frequency tables (absolute and relative frequencies) and continuous variables by summary statistics (i.e. mean, standard deviation, minimum, median, quartiles and maximum). Continuous variables will be described by absolute value and as change from baseline per analysis time point, if applicable.

All analyses will be performed for the total study population (overall analysis) and separately for PH subtype and subgroup, incident and prevalent patients, functional class at baseline, countries or regions if applicable and if patient numbers are sufficient. Prevalent patients is here defined as patients already on treatment, e.g. previously documented in the registry, whereas incident patients will be patients newly starting Adempas[®].

Patients receiving at least one dose of Adempas[®] will be included in the analysis. Whenever reasonable, data will be stratified by subgroups (e.g. age, gender).

All therapies documented will be coded using the World Health Organization – Drug Dictionary (WHO-DD). Medical history, any diseases and AEs will be coded using the latest Medical Dictionary for Regulatory Activities (MedDRA) version.

All statistical details including calculated variables and proposed format and content of tables will be detailed in the Statistical Analysis Plan (SAP). The SAP will be finalized before study database lock. The SAP is available upon request. The respective document, <7>, is listed in Annex 1.

It is planned to have at least yearly interim analysis/analyses e.g. for the purpose of the PSUR. The proportion of incident and prevalent subjects will be tracked. Analyses will refer to the primary and secondary objective. The final analysis will be performed after end of the study which is the date the analytical dataset is completely available.

All background data such as patient demographics, PH group and indication-specific characteristics and prior or concomitant medication of PH, and concomitant diseases will be described by presenting frequency distributions and/or basic summary statistics.

Sample size and disposition information by analysis time point will be displayed in a frequency table.

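### The incidence rate in Protocol 9.7.3 keeps counting treatment time after a patient's first event, so rates of common non-fatal events come out too low and fall with follow-up partly by formula

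*Protocol*

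**What the plan says.** Section 9.1.1 lists "Incidence of adverse events/ serious adverse events" as a primary endpoint, beside all-cause mortality. Section 9.7.3 sets out the analysis: "Incidences of treatment-emergent adverse events, serious adverse events and all-cause mortality will be calculated, including adverse events of interest". Two measures are given for these events. The first is a raw proportion, "number of patients with events divided by the number of treated patients", which the protocol describes as ignoring treatment time. The second is the incidence rate, "number of patients with events divided by the cumulative person-time on treatment (person-years", reported separately for incident and prevalent patients.

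Other sections bear on how the rate behaves:
- **Follow-up (9.1):** "Patients will be followed up for an observation period of 1 up to 4 years (recruitment period 3 years". On stopping, the same section says "Data collection will continue until 30 days after the end of" therapy, so a patient who has a non-fatal event and stays on the drug remains under observation.
- **Repeated looks (9.7.1):** "It is planned to have at least yearly interim analysis/analyses e.g. for the purpose of the PSUR".
- **Carry-over (9.7.4):** "The secondary safety outcomes will be analyzed similar to the primary outcomes". Kaplan-Meier plots are planned there for the adverse events of interest only.

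**The concern.** The numerator counts a patient at most once for a given event type. After the first event that patient can add nothing more to the numerator, yet the denominator goes on growing for as long as treatment continues. The result is neither a first-event rate (first events over time at risk) nor an all-event rate (all events over all time).

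The rate is there to account for unequal treatment time, which the raw proportion does not do. For a common event it does this poorly. Once most patients have had the event, the ratio approaches one divided by the mean treatment time, and so reflects length of follow-up more than risk.

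The study's primary objective is long-term safety, and the analysis is repeated on a growing database. With a constant risk, the reported rate of a common event would drift down from one report to the next and could be read as improving safety. Comparisons between subgroups or countries with different treatment durations would be distorted in the same way.

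**Working it through.** **The plan's own figure.** The protocol states no numerical incidence rate. Its only related figure is the study size in 9.5: an 83% chance of at least three patients with an event of incidence 0.5% among 900, and the same chance at 0.4% among 1130. By exact binomial, 1 − P(X ≤ 2) is 82.7% and 82.9%. Both agree with the protocol. The calculation is in proportions of patients and does not depend on the rate formula.

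**Inputs for the rate.**
- From 9.1: recruitment over 3 years and follow-up of 1 to 4 years.
- From 9.7.1: yearly looks, taken here as cumulative (assumption).
- Assumed, because the protocol is silent: even accrual, a constant first-event hazard h that is the same for all patients, and at first no discontinuation.

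**Formula.** With on-treatment time T, the expected value of the 9.7.3 ratio is E[1 − exp(−hT)] / E[T]. If person-time ends at the first event, the expected rate is h.

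**Final analysis.** T is uniform on 1 to 4 years, so E[T] = 2.5 and E[exp(−hT)] = (e^−h − e^−4h)/(3h).

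| True h per year | E[exp(−hT)] | Reported rate | Reported / true |
|---|---|---|---|
| 0.02 | 0.9514 | 0.0486/2.5 = 0.0195 | 0.973 |
| 0.1 | 0.7817 | 0.2183/2.5 = 0.087 | 0.873 |
| 0.5 | 0.3141 | 0.6859/2.5 = 0.274 | 0.549 |
| 1.0 | 0.1165 | 0.8835/2.5 = 0.353 | 0.353 |

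**Yearly looks at h = 0.5.** At years y = 1, 2, 3, T is uniform on 0 to y, so E[exp(−hT)] = (1 − e^−hy)/(hy) and E[T] = y/2.
- Year 1: (1 − 0.7869)/0.5 = 0.426
- Year 2: (1 − 0.6321)/1.0 = 0.368
- Year 3: (1 − 0.5179)/1.5 = 0.321
- Year 4 (as in the table): 0.274

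With person-time ended at first event, the expected value is 0.50 at all four looks.

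**With discontinuation.** At an assumed exponential discontinuation rate of 0.3 per year, the 9.7.3 ratio at h = 0.5 is 0.430, 0.379, 0.342 and 0.304. The fall is smaller but remains. A simulation (900 patients, h = 0.5, discontinuation 0.1 per year, 400 runs) gave 0.429, 0.372, 0.329 and 0.285 for the 9.7.3 ratio, and 0.503, 0.502, 0.501 and 0.501 for the at-risk rate.

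**When the hazard is not constant.** Two further cases, with no discontinuation:

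| Assumed hazard | Measure | Year 1 | Year 2 | Year 3 | Year 4 |
|---|---|---|---|---|---|
| Varies between patients (gamma, mean 0.5, CV 1) | 9.7.3 ratio | 0.38 | 0.31 | 0.26 | 0.22 |
| | At-risk rate | 0.44 | 0.40 | 0.37 | 0.34 |
| 1.5 per year for 3 months, then 0.3 | 9.7.3 ratio | 0.66 | 0.43 | 0.33 | 0.26 |
| | At-risk rate | 0.91 | 0.67 | 0.58 | 0.49 |

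The at-risk rate falls too, because the hazard among those still at risk falls. The 9.7.3 ratio is lower at every look and falls proportionally further. Only that extra part comes from the formula.

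**The case against.** The strongest defence is that patients with events over total exposure is a recognised exposure-adjusted measure, that the analysis is descriptive and hypothesis-generating with no test or threshold, and that 9.7.1 leaves calculated variables to the SAP. The study is sized for uncommon events, where the effect is negligible: about 0.7% at 0.005 per year and 2.7% at 0.02. Signals are assessed from case reports (11.4), and the raw proportion stands beside the rate.

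Much of this stands and limits the severity. It does not remove the point. The formula is written into the protocol as the definition of an incidence rate, so a SAP that follows it inherits the problem. In a descriptive study the descriptive figures are the whole output. The raw proportion ignores time and cannot stand in for the rate.

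A reader might infer several stronger things that the protocol does not support:
- **That this rate is the main primary measure.** Section 9.7.3 presents it together with the proportion, and specifies the preferred-term tables as proportions.
- **That the reported rate can never exceed 1/2.5 = 0.40 per year.** This needs complete follow-up. With discontinuation of 0.3 per year and h = 1.0, the final figure is 0.42.
- **That the 2-day window matters.** Events up to 2 days after treatment count while person-time stops at the end of treatment, but 2 days in 2.5 years is about 0.2% of person-time.
- **That correcting the formula makes successive reports comparable.** The varying-hazard cases show otherwise.

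**Conclusion.** The concern holds for common non-fatal events. There the 9.7.3 ratio understates the first-event rate and declines with longer follow-up partly by construction. Under a constant hazard, even accrual and no discontinuation, the final shortfall is about 13% at 0.1 per year, 45% at 0.5 and 65% at 1.0. These event rates are illustrations, since the protocol gives none. The size depends on the assumptions. The direction does not, as long as some patients stay on treatment after the event.

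All-cause mortality is unaffected, because no person-time follows death. Events that promptly end treatment are less affected. No error rate or planned decision rests on the figure, so the point is moderate and not a bar to proceeding.

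**What to change.** In 9.7.3, define the incidence rate as patients with a first event divided by person-time at risk. For each event type, end that time at the earliest of first onset, the end of the treatment-emergent window, and the end of observation. This also puts numerator and denominator on the same window. For recurrent events, total events over total on-treatment time can be added as an option. If the present ratio is also kept, label it exposure-adjusted and not an incidence rate.

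The cost is a time-at-risk derivation for each event type. No new data are needed: treatment duration is already calculated (9.7.2), and onset timing is already needed to classify events as treatment-emergent (9.7.3) and for the Kaplan-Meier plots (9.7.4). Reported rates of common AEs will be higher. The yearly reports should say that rates can still change between looks if the hazard varies over time or between patients.
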